9.4.4 SAFETY ANALYSES

N/A

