To protect against any breaches of confidentiality, all project staff proposed to conduct the data collection have received or will receive training on the protection of research participants and are or will be well versed in the Code of Federal Regulations (including 45 CFR 46 and 42 CFR) and the Belmont Report. ISA continually obtains information from the Office for Human Research Protections (OHRP) at NIH on new regulations regarding the protection of human subjects, which is disseminated to all staff. Further, participants will have the MRR procedure explained to them and will be asked to complete a medical release form before any medical records are extracted. In addition, any ISA staff proposed to work on the MRR and EHR extraction are or will be trained in all applicable HIPAA regulations.

After all participants have completed follow-up surveys, the linking file housed on the ISA computer – the only file that contains participant's personal information (e.g., name, phone number) – will be deleted. In addition, the Windows Eraser program will be used to completely remove (i.e., "wipe") the linking file from the computer by overwriting it several times using government-sanctioned deletion algorithms. Deidentified participant research data from the baseline and follow-up surveys will be retained for 3 years from the submission of the final financial report to NIH, in keeping with guidelines described in the NIH Grants Policy Statement.

The Phase II evaluation will provide very important information about the efficacy of the m-CRCSi to improve health beliefs and increase completion of recommended CRC screening tests among low SES African American men. This data is critical to developing a successful program that can help men prevent CRC or find it early when treatment is most successful. Knowledge gained from this field test will be integrated into the final program prior to marketing to FQHCs and other health care organizations. We believe that the risks associated with this Phase II effort are reasonable in relation to the valuable information we will receive.

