8.2 SAFETY ASSESSMENTS

No physical examinations, performance tests, imaging, biospecimen collection, special assays, sensors, or EMA are performed by the study. Safety procedures consist of: (1) AE/SAE identification and follow-up; (2) monitoring for distress potentially triggered by educational content; and (3) privacy/technology safeguards (e.g., wrong-number texting, shared phones). AEs are any unfavorable or unintended psychological or practical effect temporally associated with participation in the study's activities (videos, SMS, surveys), whether or not considered related. Examples include: heightened anxiety/distress about CRC risk, dissatisfaction with messaging frequency, perceived breach of privacy (e.g., texts seen by others on a shared device), or escalation of medical mistrust that prompts clinical concern. SAEs would be rare in this context and are defined per IRB policy (e.g., death, life-threatening event, hospitalization) regardless of attribution.

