8.3.3.1 SEVERITY OF EVENT

For adverse events (AEs) not included in the protocol defined grading system, the following guidelines will be used to describe severity.

- **Mild** – Events require minimal or no treatment and do not interfere with the participant's daily activities.
- **Moderate** – Events result in a low level of inconvenience or concern with the therapeutic measures. Moderate events may cause some interference with functioning.
- **Severe** – Events interrupt a participant's usual daily activity and may require systemic drug therapy or other treatment. Severe events are usually potentially life-threatening or incapacitating. Of note, the term "severe" does not necessarily equate to "serious".

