8.3.3.2 RELATIONSHIP TO STUDY INTERVENTION/EXPERIMENTAL MANIPULATION

All adverse events (AEs) will have their relationship to study procedures, including the intervention, assessed based on temporal relationship. The degree of certainty about causality will be graded using the categories below.

- **Related** – The AE is known to occur with the study procedures, there is a reasonable possibility that the study procedures caused the AE, or there is a temporal relationship between the study procedures and the event. Reasonable possibility means that there is evidence to suggest a causal relationship between the study procedures and the AE.

- **Not Related** – There is not a reasonable possibility that the study procedures caused the event, there is no temporal relationship between the study procedures and event onset, or an alternate etiology has been established.

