8.3.4 TIME PERIOD AND FREQUENCY FOR EVENT ASSESSMENT AND FOLLOW-UP

The occurrence of an adverse event (AE) or serious adverse event (SAE) may come to the attention of study personnel during study appointments.

All AEs, not otherwise precluded per the protocol, will be captured on the appropriate case report form (CRF). Information to be collected includes event description, time of onset, assessment of severity, relationship to study procedures (assessed only by those with the training and authority to make a diagnosis), and time of resolution/stabilization of the event. All AEs occurring while on study will be documented appropriately regardless of relationship. All AEs will be followed to adequate resolution.

Any medical or psychiatric condition that is present at the time that the participant is screened will be considered as baseline and not reported as an AE. However, if the study participant's condition deteriorates at any time during the study, it will be recorded as an AE.

Changes in the severity of an AE will be documented to allow an assessment of the duration of the event at each level of severity to be performed. Documentation of onset and duration of each episode will be maintained for AEs characterized as intermittent.

The study coordinator will record events with start dates occurring any time after informed consent is obtained until 7 (for non-serious AEs) or 30 days (for SAEs) after the last day of study participation. At each study visit, the investigator will inquire about the occurrence of AE/SAEs since the last visit. Events will be followed for outcome information until resolution or stabilization.

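### Section 9.4.4 plans no safety summary, so adverse events that are collected, graded and attributed are never tabulated by randomised arm

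*Combined protocol and SAP*

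**What the plan says.** The section headed "9.4.4 SAFETY ANALYSES" contains only N/A. Sections 9.3 and 9.4.1 to 9.4.3 deal with screening and survey outcomes. Section 9.4.9 (exploratory analyses) is also N/A, and Section 9.4.8 rules out listings of individual data by measure and time point.

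The safety sections describe a full collection process:

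- Section 8.2 gives as examples of AEs "heightened anxiety/distress about CRC risk, dissatisfaction with messaging frequency, perceived breach of privacy", and also growing medical mistrust that raises clinical concern.
- Section 8.3.4: "All AEs occurring while on study will be documented appropriately regardless of relationship". Onset, severity, relationship and resolution go on a case report form.
- Section 8.3.3.1 sets mild, moderate and severe grades: "the following guidelines will be used to describe severity".
- Section 8.3.3.2: "All adverse events (AEs) will have their relationship to study procedures, including the intervention, assessed based on temporal relationship".

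The stated uses of these data are reports to the IRB, NCI and OHRP (Sections 8.3.5 and 8.3.6) and the principal investigator's weekly review of AEs and SAEs and annual review of SAEs (Section 10.1.6). None is described as a summary by arm.

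**The concern.** The protocol collects structured safety data and then plans no analysis of them. The events it names are ones that could depend on how much material a man is sent and for how long, and on both counts the experimental arm can receive more. Followed as written, the plan reports screening by arm but not distress, privacy incidents or messaging complaints by arm. Section 2.3.3 foresees marketing the program to health centers and other organizations, and a center weighing adoption would want those counts. What is at stake is the completeness of harms reporting, not the efficacy result.

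**Working it through.** The plan states no safety figure, so there is none to reproduce. The check has four parts.

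**1. Is a summary by arm planned elsewhere?** Only for one named harm. Medical trust is measured at baseline and follow-up in both arms (Section 1.3), has a between-arm hypothesis (Section 9.1) and is analysed by linear regression (Section 9.4.3). A mean fall in trust would show there. Distress, privacy incidents and messaging complaints have no such outlet.

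**2. Do the arms differ in exposure?**

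- Content time (Section 1.1): about 120 minutes against 30–40 minutes. 120/40 = 3 and 120/30 = 4, so three to four times as much.
- Maximum messaging span: the experimental curriculum runs 6–9 weeks (42–63 days, Section 1.1), followed by assistance texts for up to about 116 days if screening has not occurred (Section 6.1.2). 42 + 116 = 158 and 63 + 116 = 179 days. Control runs 8 weeks (56 days, Sections 4.2, 6.1.1 and 6.1.2), or 6 weeks (42 days) by the synopsis.
- Message count: control receives 16 texts (Sections 4.2 and 6.1.1), or 1–2 a week for 8 weeks, that is 8–16 (Section 6.1.2). No experimental total is given. As an assumption only, one link for each of chapters 0–5 (6) plus the 13 assistance days named as examples gives 19; adding four Chapter 1 nudge days and three questionnaire reminders (Section 6.4) gives 26. The 13 days are examples and may come from different branches, and a man who reports screening early is closed out, so the true figure may be lower or higher.

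Other passages point the other way. Section 4.2 describes control as closely matched in delivery schedule. Section 6.2.1 plans audits to confirm equal contact frequency. The Section 1.3 table, as it reads, continues control delivery, not experimental delivery, into days 61–180, though its column alignment should be checked. These passages must be reconciled with Section 6.1.2.

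**3. Would the named events be recorded?** The definitions conflict. Section 8.2 counts any unfavorable effect associated in time with study activities, related or not. Section 8.3.1 requires the event to be unexpected, at least possibly related, and indicative of greater risk than was known. Section 8.3.4 records events whatever the relationship, and Section 8.3.3.3 classes events as expected or unexpected, which presumes that both kinds are recorded. Read strictly, Section 8.3.1 could leave foreseeable complaints off the form.

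**4. How informative would a table be?** With zero events in n men, the upper 95% bound is 1 − 0.05^(1/n) one-sided and 1 − 0.025^(1/n) two-sided.

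| Men in arm | Source | One-sided | Two-sided |
|---|---|---|---|
| 63 | Section 1.2, experimental arm | 4.6% | 5.7% |
| 77 | Section 9.2, 154/2 after attrition | 3.8% | 4.7% |
| 96 | Section 9.2, 193/2 rounded down | 3.1% | 3.8% |

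The documents give no event rates. Assume 10% experimental and 5% control. With 63 and 65 men the standard error of the difference is √(0.10×0.90/63 + 0.05×0.95/65) = 0.0465, so the 95% half-width is 1.96 × 0.0465 = 9.1 percentage points and power is about Φ(0.05/0.0465 − 1.96) = 19%. With 96 and 97 men the standard error is 0.0378, the half-width 7.4 points and power about 26%. The table would estimate rates; it could not serve as a powered comparison.

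**The case against.** The best defense is that this is a minimal-risk education trial (Section 2.3.1), where omitting a formal safety analysis is reasonable. That stands against tests or a power requirement, and neither is proposed. It does not explain why data collected to this level of detail should go unsummarised.

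Two practical objections also stand. First, ascertainment may be unequal. Staff and participants are unblinded (Section 6.3), and coordinator calls to stalled men are described only for the experimental arm (Section 6.2.1), so complaints may be heard more often there. The AE enquiry at each study visit (Section 8.3.4) applies to both arms, which limits this imbalance but does not remove it. Second, opt-outs may not be countable in both arms. Section 2.3.1 lets all participants opt out, but the STOP rule in Section 7.2 names only the experimental number, and Section 6.4 verifies delivery only for control.

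A reader might also infer more than the documents support:

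- That no harm is compared by arm. Medical trust is.
- That message volumes are known to differ greatly. Content time and maximum duration differ; the count is not given.
- That the trial cannot support its own risk-benefit judgement. The sentence "We believe that the risks associated with this Phase II effort are reasonable" is a prospective view resting on low anticipated risk, not on this trial's event rates.
- That the safety data are discarded, or that no harms will ever be published by arm. Events stay on case report forms, and Section 10.1.11 commits to submitting results to a public registry under rules whose content the documents do not give.

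**Conclusion.** The point holds in a limited form. Section 9.4.4 leaves AEs and SAEs without any planned summary by arm, although they are to be recorded, graded and attributed. Distress, privacy incidents and messaging complaints are the part left uncovered. The supported basis for expecting a possible difference is three to four times the content time and a maximum messaging span of 158–179 days against about 56; a difference in message count is not established. The precision figures rest on arm sizes of 63 to 97 and, for the two-arm calculation, on assumed rates of 10% and 5%. The effect on the primary conclusion is nil, and the priority is low.

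**What to change.** 1. Reconcile Sections 8.2, 8.3.1 and 8.3.4 into one AE definition under which the event types named in Section 8.2 are recorded in both arms.
2. Replace N/A in Section 9.4.4 with a descriptive table by randomised arm: number of men and number of events for any AE and any SAE, by severity and relatedness, and by the event types named in Section 8.2. Give exact 95% confidence intervals for the proportions of men and for their difference, and no hypothesis tests.
3. Add message opt-outs only if they are logged in both arms.
4. State beside the table that ascertainment may be unequal, and why.
5. Reconcile Sections 1.3, 4.2, 6.1.2 and 6.2.1 on contact frequency and duration, so that the table can be read against a known exposure.

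The cost is one table, minor data handling and a short clarification of definitions. The table itself adds no participants or visits and leaves the primary analysis unchanged. The drawback is imprecise estimates, which the intervals will show.

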9.4.5 BASELINE DESCRIPTIVE STATISTICS

All analyses will control for any confounding variables not managed through randomization (i.e., group difference $p < .10$).

9.4.6 PLANNED INTERIM ANALYSES

N/A

9.4.7 SUB-GROUP ANALYSES

Study intervention is only for men.

9.4.8 TABULATION OF INDIVIDUAL PARTICIPANT DATA

Individual participant data will not be listed by measure and time point.

9.4.9 EXPLORATORY ANALYSES

N/A

10 SUPPORTING DOCUMENTATION AND OPERATIONAL CONSIDERATIONS

No text is to be entered in this section; rather it should be included under the relevant subheadings below.

10.1 REGULATORY, ETHICAL, AND STUDY OVERSIGHT CONSIDERATIONS

No text is to be entered in this section; rather it should be included under the relevant subheadings below.

10.1.1 INFORMED CONSENT PROCESS

No text is to be entered in this section; rather it should be included under the relevant subheadings below.

10.1.1.1 CONSENT/ASSENT AND OTHER INFORMATIONAL DOCUMENTS PROVIDED TO PARTICIPANTS

Consent forms describing in detail the study intervention, study procedures, and risks will be given to the participant and written documentation of informed consent will be completed prior to starting the study intervention.

10.1.1.2 CONSENT PROCEDURES AND DOCUMENTATION

The field test coordinator will provide eligible men with a detailed overview of the main points of the study. First, participants will be reminded that, although health information of a sensitive nature will be included in the intervention or control materials and the survey, their names will not be associated with their survey responses or their assigned materials. The field test coordinator will also explain the flow of the study procedures and what will be asked of participants. Participants will be told that the two surveys – the baseline survey and a follow-up survey six months later – will take approximately one hour to complete. They will also be informed that their medical records will be checked again at the end of the study to verify whether they received CRC screening since the study began. Further, men will be told that half of the participants will be asked to go through the m-CRCSi after the first survey while the other half will review CRC materials developed by the CDC via a link texted to their study phone number. Those who do not go through the m-CRCSi will be given access to it after the second survey. All participants will be informed that they will complete the research surveys via telephone with the study coordinator reading the questions and recording participant responses. They will also be told that their assigned materials can all be reviewed remotely on their smartphones. Procedures for mobile phone safety will be reviewed. Finally, the field test coordinator will also explain that participants will receive \$75 for completing the baseline survey and \$100 for completing the 6-month follow-up survey. Once any participant questions are answered, eligible men will be sent a text message linking to the informed consent form. Next, the potential participant will review the informed consent document. The ISA staff member will remain on the phone while potential participants review the informed consent and will encourage them to ask any questions they may have about the study.

Men who agree to participate will acknowledge their consent by tapping a button labeled “I have read the above and AGREE to participate.” Men who choose not to participate will click a button labeled “I DO NOT AGREE and do not want to participate.” Those who choose not to participate after reading the informed consent will be thanked for their time and released. All participants will receive a copy of the text message via their preferred channel (e.g., mailed paper copy, texted PDF) for their personal records. The copy will be identical to the digital version. In addition, the consent form will have the name and toll-free telephone number of the Principal Investigator and the IRB Chairperson if participants have any additional questions.

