2.3.1 KNOWN POTENTIAL RISKS

This behavioral study (surveys plus SMS-linked educational materials) is **minimal risk**. No drugs, devices, or invasive procedures are involved; therefore package inserts or an Investigator's Brochure are not applicable. Risks align with published literature on health communication and mobile health interventions and fall into psychological and privacy domains, with negligible physical, social, legal, or economic risk.

We believe that the potential risks of collecting the survey data are small. It is possible that as a result of completing the research survey questions, a participant may learn that he is at risk for CRC. This realization may be accompanied by distress. If this should occur during the survey administration, participants will be encouraged to discuss their concerns with FMCS staff, who are trained to address these issues and to provide medical and psychological treatment as needed. They will also be provided with a list of resources in the informed consent that can provide information about CRC and recommended screening tests. To minimize this risk, participants will be completing their surveys on the computer. Their names will not be associated with their responses. In addition, the questions will be phrased in ways to minimize any potential discomfort and participants will be free to skip any question they do not wish to answer. Finally, the research team is using survey items that have been successfully used in past research with similar populations.

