4.1 OVERALL DESIGN

This is a Phase II single-site randomized, 2-arm between-subjects study examining differences in CRC screening and related beliefs between participants randomized to the experimental intervention and those randomized to the attention control condition (text messages providing CRC information and links to CDC-developed videos). Outcomes were assessed at baseline and again at 6-months post-baseline. We hypothesized that experimental participants would be more likely to get screened for CRC and report more positive beliefs about screening than control participants. Participants were assigned to conditions by an algorithm programmed into the study computer using a permuted blocks randomization scheme. Blocks of size 4 and 6 were used. Assignments within blocks was be random but balanced among the two conditions and the order of the blocks (4 vs 6) also was random. This procedure will ensure that the number of participants randomized to each condition was equal, that any imbalance among the conditions at any point during the recruitment and randomization was modest, and that it would be very difficult to guess the assignment of the next participant. Randomization was administered via computer-based admin system and triggered by the study coordinator.

The intervention – m-CRCSi – combines text messages with brief educational and motivational videos to provide CRC education, reduce screening barriers, and promote timely screening.

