6.2.1 INTERVENTIONIST TRAINING AND TRACKING

Timed text messages – called nudges – are sent to experimental participants at pre-specified intervals if they have not engaged with or completed a video chapter. After 7 days, an autodrop of the next chapter is triggered even if participants have not completed the previous chapter. Although no one “administers” the intervention content, study staff may assist with enrollment logistics and basic tech support. Staff will not advise on screening choices or alter message timing/content. If a participant becomes “stalled” (i.e., they have not engaged with intervention content in over 7 days and have not completed the intervention), an email message is sent to the study coordinator. The study coordinator then contacts the participant to inquire about any issues or questions and reinforce the importance of engaging with the intervention.

To ensure consistent delivery across arms, we will perform routine quality control (QC) checks using the SMS platform’s audit logs and dashboards. QC procedures include: (a) automated monitoring of send failures (hard/soft bounces) with daily review and same-day re-send or number verification; (b) timing-drift checks comparing scheduled vs. actual send times (tolerance ± 5 minutes for fixed-time sends; ± 24 hours for week-based sequences) with corrective action logged; (c) weekly link-uptime validation (HTTP status and redirect integrity) for all URLs in both arms, with broken links replaced from a preapproved list; and (d) parity audits to confirm equivalent contact frequency and timing windows across study arms. All QC activities are documented in an audit trail (issue, detection date, corrective action, verification). Responsibility: Study Technologist (daily automated checks) and Project Manager (weekly parity audit); oversight by the PI.

Control fidelity is tracked via delivery logs, weekly link checks, and audit reports confirming scheduled sends and link availability.

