6.3 MEASURES TO MINIMIZE BIAS: RANDOMIZATION AND BLINDING

Participants will be assigned to conditions by an algorithm programmed into the computer-based research portal. Randomization will utilize a permuted-blocks randomization scheme. Blocks of size 4 and 6 will be used. Assignments within blocks will be random but balanced among the two conditions and the order of the blocks (4 vs 6) also will be random. This procedure will ensure that the number of participants randomized to each condition will be equal, that any imbalance among the conditions at any point during the recruitment and randomization will be modest, and that it will be very difficult to guess the assignment of the next participant. Because the intervention and control materials are inherently different, participants and research staff cannot be blinded to assignment. To limit bias, primary outcome ascertainment (MRR-verified receipt of CRC screening within 6 months) will be conducted by clinic staff who abstract electronic health records without reference to group assignment; two abstractors will review each record and reconcile discrepancies, providing an additional safeguard against bias.

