6.4 STUDY INTERVENTION/EXPERIMENTAL MANIPULATION ADHERENCE

Participants’ adherence is tracked entirely through platform telemetry. During the curriculum phase, the SMS system records each linked video open and completion at the chapter/video level, issues time-based nudges when progress stalls (e.g., Day 2/4/6/7 rules for Chapter 1), and—if needed—auto-advances to the next assessment to preserve momentum. In the post-education phase, completion of the brief status questionnaire is monitored; automated reminders are sent at 2, 4, and 5 days if incomplete. Thereafter,

scheduled check-ins and resources continue on a fixed cadence (extending to ~116 days for noncompleters), and participant replies (including the keyword SCREEN) are logged as adherence signals and to close out the program when screening is reported.

Mandatory activities to remain an active participant are: consent, baseline questionnaire completion, randomization, and provision of a working mobile number (to enable delivery). All subsequent educational exposures (video views) and assessments are encouraged and tracked but not required for continued participation; the system's escalation (nudges/auto-drops) is designed to maximize exposure without removing participants for nonresponse.

Source records for adherence include the SMS platform logs (timestamps, message types, opens/completions, replies) and assessment completion flags. Optional activities available to participants (and tracked when used) include engaging the built-in reminder system and revisiting resources/videos; use is captured by link launches and elapsed time triggers.

No in-person visits are required for adherence. For transparency in reporting dose/exposure, we will summarize: number of curriculum videos delivered/opened, assessment completion and days-to-completion, number of SMS messages delivered and proportion eliciting a reply, days retained in the assistance stream, and whether/when screening was confirmed via SMS.

Control-arm adherence (e.g., link click-throughs or time on page) is not collected. To minimize participant burden and maintain parity with standard informational outreach, we verify delivery only, using SMS send logs. Primary analyses are intention-to-treat and do not rely on control exposure metrics.

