- **Follow-up questionnaire:** repeat of key psychosocial measures to explore mechanisms and acceptability.

Outcome definitions (non-safety)

- **CRC screening completion:** Documentation in the medical record or self-report of colonoscopy, FIT, FIT-DNA, CT colonography, or flexible sigmoidoscopy performed within the 6-month window (plus any pre-specified grace period).

- **Exposure/dose metrics:** Number of SMS delivered; proportion eliciting a response; number/proportion of videos opened by chapter; completion of the immediate post-education questionnaire; and elapsed days in PESA until closeout.

Administration, scoring, and data quality

- **Administration.** All questionnaires are administered via telephone.
- **Scoring.** Multi-item scales are scored per codebook (sum or mean of valid items; higher scores reflect greater endorsement or knowledge, as defined). Missing-data rules (e.g., minimum items required) are pre-specified.
- **Data capture.** Survey responses and SMS telemetry are time-stamped and stored on the study platform; MRR uses standardized abstraction forms with dual review and reconciliation.

Qualified personnel

- **MRR:** Conducted by trained study staff (e.g., clinic research coordinators) using a standardized abstraction guide; complex clinical ambiguities are adjudicated by a qualified clinician (e.g., physician or advanced practice provider).
- **Telephone-based assessment:** Conducted by trained study staff.

Use of existing clinical data and HIPAA

The study uses existing medical charts to verify CRC screening. HIPAA, applicable federal/state laws, and local institutional requirements are followed. MRR variables include test type and date (and result if available). No central lab is used; no CLIA-covered testing is performed by the study.

Standard of care procedures

All screening tests are ordered and performed as part of routine clinical care, independent of the research team. The study does not alter clinical pathways, rescue therapy, or provider decision-making.

Results returned to participants

Participants receive general educational messages and resource links through the intervention or control SMS sequences. The study does not generate new clinical test results; any clinical results (e.g., from a colonoscopy) are communicated by the healthcare system per usual care.

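### The 6-month survey is read out and recorded by an unblinded coordinator role that also triggers randomisation and calls stalled experimental men, with no safeguard for survey endpoints and a conflicting account of survey mode in 2.3.1

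*Combined protocol and SAP*

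**What the plan says.** **Who asks.** Under section 10.1.1.2, men are told that "they will complete the research surveys via telephone with the study coordinator reading the questions and recording participant responses". Section 8.1 agrees on mode: "All questionnaires are administered via telephone". On personnel it says only "Conducted by trained study staff".

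**What else that role does.** Section 4.1: "Randomization was administered via computer-based admin system and triggered by the study coordinator". Section 6.2.1, on men who have stopped engaging with the content: "The study coordinator then contacts the participant to inquire about any issues or questions and reinforce the importance of engaging with the intervention".

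**Blinding.** Section 6.3 states that "participants and research staff cannot be blinded to assignment". To limit bias it has clinic staff abstract the records without reference to arm, with two abstractors per record. It gives no equivalent measure for the survey.

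**Conflicting mode.** Section 2.3.1, discussing distress from the survey questions, says: "To minimize this risk, participants will be completing their surveys on the computer".

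**What the survey supplies.** Sections 1.3, 8.1 and 9.1 take from it the severity, susceptibility, benefit and barrier scales, CRC knowledge, self-efficacy, medical trust and the self-reported screening composite.

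**The concern.** At 6 months a man gives his answers aloud to someone in a role that knows his arm and, in one arm only, may already have pressed him to engage with the programme. Attitude scales and self-reported behaviour can respond to who is asking. If that influence differs by arm, it enters the arm comparison directly, and nothing in the plan prevents, measures or discloses it.

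The conflict over mode adds a second problem. Section 2.3.1 offers self-completion on a computer as a protection for participants, while the procedures sections describe a spoken interview. A reader cannot tell which was delivered, or whether the stated protection existed.

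**Working it through.** The plan gives no bias figure to reproduce, so the check is mainly a comparison of sections. A sensitivity calculation on assumed bias sizes follows.

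**Step 1. Is the interviewer aware of arm?** 10.1.1.2 assigns the survey to the study coordinator, 4.1 has that role trigger randomisation, and 6.3 says research staff are unblinded. No section hides arm from the interviewer or separates the tasks.

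**Step 2. Is prior contact one-sided?** In 6.2.1 the nudges go to experimental participants, and a stall means more than 7 days without engaging with the intervention. Section 6.4 says control engagement is not collected, so no control man can be flagged as stalled.

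**Step 3. Does it cancel in change scores?** Section 8.1 places the baseline survey before randomisation, so knowledge of arm can affect only follow-up. If follow-up answers in the experimental arm shift by b, the difference in change is

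(F_E + b − B_E) − (F_C − B_C) = true difference + b.

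It does not cancel.

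**Step 4. Are the accounts of mode compatible?** 2.3.1 has participants themselves using a computer. 8.1 and 10.1.1.2 have all questionnaires given by telephone, with staff recording. These cannot both describe the same survey.

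**Step 5. How much could a shift matter? (bias sizes assumed)**

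Inputs from section 9.2: self-efficacy 3.89 (SD 0.84) against 3.64 (SD 1.00); 154 analysed, so 77 per arm; screening 34% against 19%. From the schema in 1.2: 128 in total, so 64 per arm on average (63 and 65), with no losses assumed.

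The plan's effect size reproduces: 0.25 / √((0.84² + 1.00²)/2) = 0.25 / 0.92 = 0.27.

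*One scale.* Take no true effect, a two-sided 5% t-test, and a shift of b SD in one arm. The statistic is noncentral t with 2n − 2 degrees of freedom and noncentrality b√(n/2). For b = 0.2 and n = 77 this is 0.2 × √38.5 = 1.24.

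| Shift b (SD) | False positives, 77 per arm | 64 per arm |
|---|---|---|
| 0 | 5% | 5% |
| 0.1 | 9.5% | 8.7% |
| 0.2 | 23% | 20% |
| 0.27 | 38% | 33% |

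The table is symmetric: a shift of the same size against the intervention gives the same rate in the other direction.

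*Self-reported screening.* Take a true 19% in both arms and let a fraction q of unscreened men in one arm over-report. That arm then reports 0.19 + 0.81q. The test is a pooled two-proportion z-test.

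| q | Reported rate | False positives, 77 per arm | 64 per arm |
|---|---|---|---|
| 5% | 23.1% | 9% | 9% |
| 10% | 27.1% | 22% | 19% |
| 15% | 31.1% | 41% | 35% |

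Creating the whole 19% to 34% difference would need q = 0.15 / 0.81 = 18.5%.

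These tables show sensitivity. They do not estimate the bias in this trial.

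**The case against.** **Telephone administration is defensible.** The surveys take about an hour (10.1.1.2) and section 2.2 raises health literacy. Self-completion could cost missing items and attrition. Changing mode only at follow-up would mix mode with change in the 9.1 hypotheses. This stands, and it is why the fix does not require self-completion.

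**The documents name a role, not a person.** Section 8.1 says only trained study staff, and 5.5 and 10.1.1.2 also use the title field test coordinator. The number of stall calls is not given, and 6.2.1 bars staff from advising on screening choices. This also stands: the exposure is documented, but its extent is not.

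**Self-report can be partly checked.** Section 9.3 expects medical releases for all participants, so self-report can be set against the MRR by arm, although tests done elsewhere may be missed. Men are also told that their records will be checked, which discourages over-reporting. It would be too strong to say that an interviewer effect on this endpoint could never be detected. No such check exists for the belief and trust scales.

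A reader might infer four stronger points that the documents do not support:

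- *That the bias favours the intervention.* This is plausible, but it is an inference. Both arms receive CRC education and answer to the same role.
- *That experimental men have a second self-report route through the SMS keyword.* Section 6.4 lists "whether/when screening was confirmed via SMS" among dose and exposure summaries, and 8.1 places keyword replies under process data. Nothing says that they feed the outcome.
- *That 2.3.3 repeats the contradiction.* A computer-based survey tool is compatible with a coordinator entering telephone answers directly into the database (10.1.8). Only 2.3.1 has participants themselves at the computer.
- *That the MRR-verified result is compromised.* Its abstraction is done without reference to arm. Sections 3 and 8.1 do mention self-report in defining screening completion. That is a separate question of endpoint definition, and any self-reported component would carry this exposure with it.

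**Conclusion.** The concern holds as a gap in outcome assessment for the survey endpoints. An unblinded role with randomisation and one-sided engagement duties collects every belief, knowledge, self-efficacy and trust score and the self-reported screening composite, and the plan's only safeguard does not reach them. CRC knowledge is probably less susceptible than the attitude scales if it is scored on correct answers. The conflict between 2.3.1 and sections 8.1 and 10.1.1.2 needs no inference and must be reconciled in any case.

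The direction and size of any bias are unknown. Under assumed one-arm shifts of 0.1 to 0.2 SD, a single scale's false-positive rate would be about 9% to 23% instead of 5%, depending on whether 64 or 77 men per arm are analysed. That is enough to matter for secondary claims.

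**What to change.** 1. Reconcile 2.3.1 with 8.1 and 10.1.1.2 on survey mode, and use the same mode at baseline and 6 months.
2. In 6.3, 8.1 and 10.1.1.2, require that any telephone follow-up survey be done by an existing team member who did not randomise that man, made no stall calls and works from a survey screen that does not show arm. Record the interviewer and any unblinding during the call.
3. State that self-reported screening is taken only from the 6-month survey in both arms, and compare it with the MRR by arm.
4. Sections 1.2, 2.1 and 4.1 already report numbers per arm or conduct in the past tense. If follow-up is complete, items 1 and 2 reduce to an accurate account of what was done: state in 6.3 that these endpoints were collected by an unblinded interviewer, and limit the claims made from them. Item 3 remains possible.

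The cost is protocol wording and reassigning survey or stall calls among existing staff. Participants remain unblinded, so some desirability bias may persist.
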